## 4 Additional details on implementation of statistical methodology

The sections below contain additional details on statistical methodology that will be included in [Appendix 16.1.9](#) (Documentation of Statistical Methods) of the CSR as well as rules details on programming rules that will be followed to implement the analyses described in [Section 2](#).

### 4.1 Data included in the analyses

This section provides additional details to those included in [Section 2.1](#).

Each analysis (primary analysis and final analysis) will include the data with an assessment date or event start date (e.g. vital sign assessment date or start date of an adverse event) prior to or on the cut-off date. For example, if the cut-off date is 30DEC2008, an AE starting on 28DEC2008 will be reported, whereas an adverse event starting on 31DEC2008 will not be reported.

### 4.2 Last contact date

The last contact date will be derived for patients not known to have died at the analysis cut-off using the latest complete date among the following:

- All patient assessment dates (e.g. blood draws (laboratory, [REDACTED]), vital signs, performance status, ECG, tumor assessments)
- Start and end dates of antineoplastic therapies administered after study drug discontinuation (with non-missing medication/procedure term).
- AE start and end dates (with non-missing verbatim AE term present)
- From ‘Survival information’ eCRF:

- Last known date patient alive if answer to question ‘Is subject alive?’ is ‘lost to follow-up’;
- Date of assessment if answer to question ‘Is subject alive?’ is Yes  
Note: If answer to question ‘Is subject alive?’ is ‘unknown’, neither ‘last known date patient alive’ nor ‘date of assessment’ is used
- Study drug start and end dates from DAR with non-missing dose. Doses of 0 are allowed.
- Concomitant medications/Surgical and Medical Procedures start and end dates
- Date of discontinuation/study phase completion on the ‘End of treatment discontinuation’ and the ‘End of Post Treatment Phase Disposition’ eCRFs.

The last contact date is defined as the latest complete date from the above list on or before the data cut-off date. The cut-off date will not be used for last contact date, unless the patient was seen or contacted on that date. Completely imputed dates (e.g. the analysis cut-off date programmatically imputed to replace the missing end date of a dose administration record) will not be used to derive the last contact date.

Only dates associated with patient visits or actual examinations of the patient will be used in the derivation. Dates associated with a technical operation unrelated to patient status such as the date a blood sample was processed will not be used. Assessment dates after the cutoff date will not be applied to the last contact date.

Partial date imputation is allowed for event (death)/censoring if the date is coming from ‘Survival information’ eCRF only. If the day is missing for the ‘Date of assessment’ when answer to question ‘Is subject alive?’ is Yes, or ‘Last known date patient alive’ when answer to question ‘Is subject alive?’ is ‘lost to follow-up’, it will be imputed to 1st day of the month and year. If imputed date is after cut-off date, then this date will not be applied to derive the last contact date.

### 4.3 Month derivation

For all derivations, a month will be calculated as  $(365.25 / 12) = 30.4375$  days. If duration is to be reported in months, duration in days will be divided by 30.4375.

### 4.4 Age derivation

Age for enrolled patients or screen failures will be calculated based on the date when the patient signed the main study informed consent from the date of birth.

### 4.5 Dose interruptions and dose changes

This section provides additional details to those included in [Section 2.6](#). Both dose interruption and dose change are analyzed based on CRF pages based on the dose actually taken by the patients.

An interruption is defined as a 0 mg dose taken on one or more days. What follows defines how dose interruptions will be counted in the case of multiple dose interruptions.

- If an interruption occurs consecutively for at least two days due to the same reason, then it will be counted only once (*example: If the actual dose on days 1-3 is 750 mg and actual*

*dose on days 4-5 is 0 mg and dose interruption on days 4-5 is due to AE, then the total number of dose interruptions is 1).*

- If an interruption occurs consecutively for at least two days due to different reasons, then it will be counted for each reason (*example: If the actual dose on days 1-3 is 750 mg and actual dose on days 4-5 is 0 mg and dose interruption on day 4 is due to AE and dose interruption on day 5 is due to dosing error, then the total number of dose interruptions is 2).*
- If an interruption occurs for more than one day due to the same reason, but the days are not consecutive, i.e. there is at least one dosing day in between, then each dose interruption will be counted as a different occurrence (*example: if the actual dose on days 1, 3 and 5, is 750 mg and actual dose on days 2 and 4 is 0mg, and dose interruptions on day 2 and 4 are both due to dosing error, the total number of dose interruptions is 2).*

A dose change is defined as a change in dosing from one record to the next. However, a dose interruption will not be counted as a dose change. For example, for LDK378, in the sequence 750 mg – 0 mg – 600 mg, the 600 mg dose will be counted as a dose change (with reason documented), preceded by a 0 mg due to interruption (with reason documented). Dose reductions are a subset of dose changes where dose changes to higher than protocol planned dose are excluded.

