6.3.3 Criteria for ceritinib dose modifications

A ceritinib dose reduction will follow the guidelines described in [Table 6-2](#). For each patient, a maximum of 3 dose modifications (in 150 mg decrements per reduction) is allowed after which the patient must be discontinued from treatment with ceritinib. Once the dose of ceritinib has been reduced, it cannot be re-escalated. If a patient continues treatment with ceritinib after RECIST-defined PD as determined by the investigator, the criteria for dose modification will also apply.

[figure not shown]

Table 6-2 Dose reduction steps for ceritinib

[figure not shown]
Ceritinib dose levels	Dose* and schedule
Starting dose level	750 qd continuously
Dose level – 1	600 qd continuously
Dose level – 2	450 qd continuously
Dose level – 3	300 qd continuously **

*Dose reduction should be based on the worst preceding toxicity per NCI-CTCAE version 4.03
**Dose reduction below 300 mg/day is not allowed. If a dose reduction below 300 mg/day is required, the patient should be permanently discontinued from Ceritinib

[figure not shown]
Guidelines for dose modification and dose interruption of ceritinib are described in [Table 6-3](#).

Table 6-3 Criteria for dose reduction, interruption and re-initiation of ceritinib treatment

[figure not shown]
Worst toxicity (CTCAE 4.03 Grade)*	Dose Modifications for ceritinib
HEMATOLOGICAL	
Neutropenia (ANC)	
Grade 1 (ANC < LLN - $1.5 \times 10^9/L$) Grade 2 (ANC < 1.5 and $\geq 1.0 \times 10^9/L$) Grade 3 (ANC < 1.0 and $\geq 0.5 \times 10^9/L$)	Recommendation: Maintain dose level
Grade 4 (ANC < $0.5 \times 10^9/L$)	Mandatory: Omit dose until resolved to \leq Grade 2, then it is recommended: If resolved in ≤ 7 days, to maintain dose level If resolved in > 7 days, to \downarrow 1 dose level
Febrile neutropenia (ANC < $1.0 \times 10^9/L$, with a single temperature of ≥ 38.3 °C or a sustained temperature of ≥ 38 °C for more than one hour)	Mandatory: Omit dose until clinically resolved and neutropenia \leq Grade 2, then \downarrow 1 dose level
Thrombocytopenia	
Grade 1 (PLT < LLN - $75 \times 10^9/L$) Grade 2 (PLT < 75 and $\geq 50 \times 10^9/L$)	Recommendation: Maintain dose level
Grade 3 (PLT < 50 and $\geq 25 \times 10^9/L$)	Mandatory: Omit dose until resolved to \leq Grade 2, then it is recommended: If resolved in ≤ 7 days, to maintain dose level If resolved in > 7 days, to \downarrow 1 dose level

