10.5.3.5 Tolerability

Tolerability will be summarized in terms of dose reductions or drug interruption due to an AE.

[figure not shown]
[figure not shown]

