## Dose exposure and intensity

Definitions of duration of exposure, cumulative dose, average daily dose, dose intensity (DI), relative dose intensity (RDI), as well as intermediate calculations, include:

- Duration of exposure (days): last date of study drug – first date of study drug + 1 (periods of interruption are not excluded)
- Cumulative dose (mg): total dose of study drug taken by a patient in the study
- Number of dosing days (days): duration of exposure – number of zero dose days

- Average daily dose (mg/day): cumulative dose (mg)/ number of dosing days (days)
- DI (mg/day): cumulative dose (mg)/ duration of exposure (days)
- RDI (%):  $100 \times [\text{DI (mg/day)}/\text{planned dose intensity (750 mg/day)}]$

Note: given the planned ceritinib dose of 750 mg/day, the planned dose intensity can be calculated as:

$$\text{PDI (mg/day)} = \text{cumulative planned dose (mg)}/\text{Duration of exposure (days)},$$

where

$$\text{cumulative planned dose (mg)} = \text{Protocol planned dose of 750 (mg)} * \text{Duration of exposure.}$$

then, RDI (%) which is calculated as  $100 * \text{DI}/\text{PDI}$  can be simplified as shown above.

Duration of exposure to study drug, cumulative dose, average daily dose, DI and RDI will be summarized by study arm and for all patients. In addition, the duration of exposure to study drug will be categorized into time intervals and frequency counts and percentages of patients with exposure in each time interval will be presented. Frequency counts and percentages of patients who have dose changes, reductions or interruptions, and the corresponding reasons, will be summarized by study arm and for all patients. Time to first dose reduction and time to first dose interruption will be summarized by study arm and for all patients, using summary statistics along with frequency counts and percentages for pre-specified time intervals

Listings of all doses of the study drug along with dose change and dose interruption reasons will be produced.

[Section 4.5](#) provides further details on the definition of dose changes and interruptions.

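### SAP 4.5 defines a dose reduction without requiring the dose to fall, so an upward change ending at or below 750 mg is classed as a reduction

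*SAP*

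**What the plan says.** SAP 4.5 builds its terms in three steps. First, "A dose change is defined as a change in dosing from one record to the next", with no direction given. Second, "However, a dose interruption will not be counted as a dose change", illustrated by the sequence 750, 0, 600 mg, in which the 600 mg record is the dose change. Third, "Dose reductions are a subset of dose changes where dose changes to higher than protocol planned dose are excluded". The data are doses taken: "Both dose interruption and dose change are analyzed based on CRF pages based on the dose actually taken by the patients". The planned dose is 750 mg/day (SAP 2.6, dose exposure and intensity).

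The opening of SAP 4 says that the section holds the programming rules to be followed and that its details go into Appendix 16.1.9 of the CSR. SAP 2.6 names the outputs that use the definition: the number and percentage of patients with dose changes, reductions or interruptions, the corresponding reasons, and the time to first dose reduction.

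The protocol uses the term directionally. Section 6.3.3 says that "a maximum of 3 dose modifications (in 150 mg decrements per reduction) is allowed" and that "Once the dose of ceritinib has been reduced, it cannot be re-escalated". Protocol 10.5.3.5 adds: "Tolerability will be summarized in terms of dose reductions or drug interruption due to an AE".

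**The concern.** A reduction ought to mean that the dose went down. The SAP sentence removes only changes to a dose above plan. Every other change stays in, whichever way it went, and neither document gives a directional definition for the analysis.

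The bar on re-escalation does not rule out upward records, because the derivation uses the dose taken. Two routes are plausible:

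- **Partial-dose day.** Protocol 6.1.1 tells a patient who has not taken the full dose to leave out the rest and continue with the next scheduled dose. If the short day is a separate dosing record, the return to 750 mg the next day follows the protocol, yet the SAP classes it as a reduction.
- **Low start.** A patient started below 750 mg in error and then corrected upward is classed as reduced.

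The reason recorded for such an upward change would be tabulated as a reason for dose reduction.

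**Working it through.** The plan states no figure to reproduce, so the check applies the written rule to dose sequences.

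**Inputs.** Planned dose 750 mg (SAP 2.6). Protocol dose levels 750, 600, 450 and 300 mg (Protocol Table 6-2). Definitions from SAP 4.5.

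**Rules compared.**
- As written: reduction = dose change with new dose ≤ 750 mg.
- Directional: reduction = new non-zero dose < last non-zero dose, and new dose < 750 mg.

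**Transitions between protocol levels.** There are 4 × 3 = 12 ordered pairs. Each ends at or below 750 mg, so 12 of 12 are reductions as written. Half go down, so the directional rule gives 6 of 12. The other 6 are increases.

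**Example sequences** (as-written column compares with the last non-zero dose):

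| Doses (mg) | As written | Directional |
|---|---|---|
| 750, 0, 600 (SAP example) | 1 | 1 |
| 750, 600, 450, 300 | 3 | 3 |
| 750, 600, 750 | 2 | 1 |
| 750, 600, 450, 600 | 3 | 2 |
| 600, 750 (low start) | 1 | 0 |
| 750, 0, 750 | 0 | 0 |
| 750, 900, 750 | 1 | 0 |

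If a resumed dose is instead compared with the 0 mg record, 750, 0, 750 gives 1 as written.

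**Effect on the patient-level outputs.** Suppose the first recorded dose is 750 mg, no dose exceeds 750 mg, and each dose is compared with the last non-zero dose. An increase ending at or below 750 mg must start below 750 mg, so a decrease must have come earlier. The any-reduction flag and the date of the first reduction are then the same under both rules. Enumerating all sequences of 2 to 5 records that start at 750 mg, with later doses of 0, 300, 450, 600 or 750 mg (5 + 25 + 125 + 625 = 780 sequences), gives no disagreement on either.

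Two conditions break this agreement:
1. The first recorded dose is below 750 mg (600, 750).
2. The resumed dose is compared with 0 mg (750, 0, 750). SAP 4.5 does not say which comparison applies, and Protocol 6.3.2 allows treatment to resume at the same dose after an interruption for reasons other than toxicity, so this sequence is to be expected.

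A boundary case is a dose above plan corrected to 750 mg (750, 900, 750). That change is downward, but it does not take the patient below plan. The written rule counts it, and so would a fix that asked only for a dose lower than the previous one. The directional rule above does not.

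**The case against.** The strongest reply concerns consequence. Every patient is planned to start at 750 mg, re-escalation is barred, and nothing in the documents shows that an upward change occurred. Whether a partial-dose day becomes its own record depends on eCRF completion rules that are not in the documents. All of this stands, and it is why the effect is probably small. It does not make the rule right, because the sentence is an explicit programming rule.

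Three stronger readings are tempting, and the documents support none of them.

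- **Inflated number of reductions per patient, or a distorted split between one and several.** The count does change (750, 600, 750 gives 2 instead of 1), but SAP 2.6 plans no table of reductions per patient. It plans patient-level counts, reasons and time to first reduction.
- **Sizing the error from the earlier ceritinib study.** Protocol 1.2.1.2.1 reports reductions in 58.4% of patients, with 38.8% having only one. Those are reductions due to adverse events in another study, derived by a rule that cannot be seen. They do not show how often an upward change would be misclassified here.
- **Corruption of the protocol's tolerability measure.** Protocol 10.5.3.5 names reductions or interruption, and ties them to an adverse event. An upward correction would not normally carry an adverse-event reason. The summaries of adverse events requiring dose adjustment or interruption (SAP 2.8.2) do not depend on the SAP 4.5 sentence.

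**Conclusion.** The definition is wrong as written: it classes any upward change ending at or below 750 mg as a dose reduction. The reasons for reduction are the planned output most exposed. The percentage of patients with any reduction and the time to first reduction hold for patients who start at 750 mg and never exceed it, if doses are compared with the last non-zero dose. They fail after a low first dose or under comparison with a 0 mg record, and a corrected overdose is also counted.

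The size cannot be computed, because the documents do not say how many upward changes, low starts or separately recorded partial days there were. The judgement that it is small rests on the bar on re-escalation and the common 750 mg starting dose. No efficacy endpoint uses this definition. This is a minor point, worth correcting because correction is cheap.

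**What to change.** Replace the sentence in SAP 4.5 with a definition of this kind: a dose reduction is a dose change in which the new non-zero dose is lower than both the last preceding non-zero dose and the planned 750 mg. Add that resuming the same dose after a 0 mg record is not a dose change. The SAP's own example (750, 0, 600 mg) still gives one reduction, and a return from above 750 mg to 750 mg gives none.

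Listing single-day partial doses separately is optional and not needed for the correction.

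The cost is about two sentences and a small change to the derivation program, with no new data. The change concerns only how doses are classified in the analysis.

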## 4.6 Efficacy endpoints

For further details on efficacy endpoints, see [Section 14](#) (Appendixes 2 and 3) of the LDK378A2205 protocol. For the evaluation of tumor-response related endpoints, response is assessed by investigator and BIRC according to RECIST 1.1 with the exception of intracranial endpoints following Modified RECIST 1.1. Additionally, intracranial endpoints are also evaluated by investigator and BIRC as exploratory endpoints according to RANO criteria.

The text below gives more detailed instructions and rules needed for programming of the analyses described in [Sections 2.7](#) and [2.8.1](#).

### 4.6.1 Implementation of RECIST guidelines

#### Disease progression

PD should only be assigned if it is demonstrated by an objective assessment method as per RECIST 1.1 (whole body and extracranial) or Modified RECIST 1.1 (intracranial) (e.g. radiologic scan, histology for bronchoscopy, photos for skin lesions). If a new lesion is detected using an objective assessment method other than radiologic scan, it should be entered on the 'New lesion' RECIST eCRF with appropriate method (or method='Other').

In particular, discontinuation due to disease progression or death due to progressive disease, without supporting objective evidence (as defined above), will not be considered as PD in the determination of BOR, the derivation of any efficacy endpoint or efficacy analysis.

#### Change in imaging modality

Per RECIST 1.1, a change in methodology can be defined as either a change in contrast use (e.g. keeping the same technique, like CT, but switching from with to without contrast use or vice-versa, regardless of the justification for the change) or a change in technique (e.g. from CT to

MRI, or vice-versa), or a change in any other imaging modality. A change from conventional to spiral CT and vice versa while keeping same contrast use (e.g. switching from spiral CT with contrast to CT with contrast) is not considered a change in imaging modality .

A change in methodology will result by default in a UNK (unknown) overall lesion response assessment. However, a response assessment other than the Novartis calculated UNK response may be accepted from the investigator or BIRC if a definitive response assessment can be justified based on the available information. Potential discrepancies between the modality used and overall lesion response reported by the investigator (e.g. change in modality but investigator assessment of response is different from UNK) will be queried during the data validation process.

### **Determination of missing adequate tumor assessments**

For the computation of ORR (for primary analysis), patients without any radiological assessment after the start date of study drug will be counted as failure.

Partial or complete responses reported prior to any additional anticancer therapy will be considered for ORR computation irrespective of the number of missed assessments before response. The anticancer therapy will be defined for intracranial, extracranial and whole body separately: e.g., radiotherapy to the brain will only be considered as anticancer therapy for intracranial and whole body endpoints but not for extracranial endpoint. In this section, the ‘missing adequate assessment’ is defined as assessment not done or assessment with overall lesion response equal to UNK. For the sake of simplicity, the ‘missing adequate assessment’ will also be referred as ‘missing assessment’.

As detailed in [Section 14](#) (Appendix 2) of the LDK378A2205 protocol and [Table 2-2](#) of SAP, the PFS censoring and event date options depend on the presence and the number of missing tumor assessments. *For example, an event occurring after two or more missing assessments is censored in the analysis of PFS at the last adequate tumor assessment before the event date.*

An exact rule to determine whether there is none, one or two missing assessments is therefore needed. This rule will be based on the distance between the last adequate tumor assessment date and the event date.

If the distance is larger than threshold  $D_1$  or  $D_2$  then the analysis will assume one or two missing assessments, respectively. The threshold  $D_1$  will be defined as the protocol specified interval between the tumor assessments plus the protocol allowed window around the assessments. Similarly, the threshold  $D_2$  is defined as two times the protocol specified interval between the tumor assessments plus the protocol allowed window around the assessments. In this study, the protocol defined schedule of tumor assessment is every 8 weeks and each assessment is expected to be performed at the scheduled time point plus or minus 1 week, i.e. the window is 2 weeks, then any distance larger than  $D_1 = 8 + 2 = 10$  weeks means one missing assessment and any distance larger than  $D_2 = (2 * 8) + 2 = 18$  weeks means two missing assessments.

The same definition of  $D_2$  will be used to determine the PFS censoring reason.

Possible censoring reasons for PFS are:

1: Ongoing without event

2: Lost to follow-up

CONFIDENTIAL - For Business Use Only

- 3: Withdrew consent
- 4: Adequate assessment no longer available
- 5: Event after  $\geq 2$  missing tumor assessments

**Non-measurable disease at baseline**

As specified in Section 14 (Appendix 2) of the LDK378A2205 protocol, the RECIST 1.1 criteria imply that only patients with measurable disease at baseline (at least one extracranial measurable lesion as per inclusion criteria) should be included in the study. If a patient without measurable disease is enrolled, the intent-to-treat (ITT) principle requires including these patients in the analyses. Hence, analyses will be based on FAS including patients with either measurable or non-measurable disease. Therefore, a rule needs to be specified on how to handle these cases.

As specified in Table 3-1 of Section 14 (Appendix 2) of the LDK378A2205 protocol, overall lesion response can be derived for patients without measurable disease at baseline as follows (Table 4-1).

